3 RATIONALE

3.1 RATIONALE FOR STUDY DESIGN

Total abdominal radical hysterectomy (TARH) and pelvic lymph node dissection (± aortic lymph node dissection ± postoperative [chemo-] radiotherapy) is the current standard treatment for early cervical cancer. While this is an accepted effective treatment, a laparotomy is highly invasive, visibly scarring and is associated with tissue trauma, blood loss and a significant risk of wound and infectious adverse events⁷⁴ ⁷⁵. Additionally, radical hysterectomy by laparotomy is associated with an average hospital stay of approximately 5 to 7 days and an average recovery period (from surgery) of 5 to 6 weeks.

Laparoscopic techniques have been demonstrated to be feasible and safe with previous retrospective studies on TLH showing encouraging results⁷⁶. In a number of retrospective and prospective, non-controlled series the incidence of treatment-related morbidity was less in patients who had a laparoscopic hysterectomy compared to patients who underwent a TAH⁷⁷. Retrospective data suggest that the recurrence rate and patterns of recurrence are similar in patients who had a laparoscopic or an open approach⁷⁸.

Treatment recommendations ideally are based on prospective, randomized trials comparing the current standard technique (TARH) with the proposed better technique (TLRH). However, there are currently no prospective studies available which directly compare TLRH against the standard treatment of TARH in regards to disease-free or overall survival.

The proposed clinical trial will be biphasic. The primary outcome variable in stage 1 will be feasibility of recruitment as determined by overall trial recruitment. Following completion of Stage 1, the data of this study will become the basis for assessing recurrence and disease-free survival in the Stage 2 design.

3.2 RATIONALE FOR THE QUALITY OF LIFE

Retrospective studies suggest equivalency between the laparoscopic and open approaches to radical hysterectomy in regards to surgical specimens obtained ⁷⁹ and likely disease-free and overall survivals ⁸⁰ ⁸¹ ⁸² ⁸³ ⁸⁴ ⁸⁵ ⁸⁶. Thus, quality of life could be seen as one of the most significant factors in recommending one approach over the other and therefore an extremely important endpoint for this protocol. In the GOG LAP-2 protocol⁸⁷, a trial evaluating a comparison between hysterectomy by laparotomy or laparoscopy, the investigators found equivalency adequacy of the two surgical approaches however a significant difference in short term quality of life favoring laparoscopy. As expected, patients who underwent laparoscopy had a faster return to baseline functioning compared with those patients who had undergone laparotomy which translated into improved short-term quality of life. By 6 months, however, patients in both cohorts were reporting equivalent quality of life parameters. Quality of life surveys employed with this Phase III clinical trial will encompass important endpoints such as postoperative pain and related symptoms using the MD Anderson Symptom Assessment Index (MDSAI), as well as cancer specific Functional Assessment of Cancer Therapy (FACT-Cx) and the general 12-Item Short-Form Health Survey (SF-12).

3.3 RATIONALE FOR LYMPHATIC MAPPING

Published experience with the techniques for lymphatic mapping and sentinel lymph node detection in women with cervical cancer has been very limited. To date, no single study has enrolled more than 100 patients undergoing lymphatic mapping as part of their surgical treatment for cervical cancer. In fact, the majority of studies report on less than 50 patients. In addition, this procedure has not yet been shown to be viable in a multi-institutional setting. The limitations of previously published reports are important as these techniques are associated with a significantly high learning curve with early procedures less successful than later ones. This study will provide us the opportunity to enroll large numbers of patients for validation of intraoperative lymphatic mapping in women with cervical cancer in an international, multi-institutional setting.

3.3.1 DRUG INFORMATION:

Isosulfan Blue (Lymphazurin®)

- Formulation: Sterile aqueous solution in 5 ml vials.
- Preparation: None.
- Storage: Room temperature, avoid excess heat.

Supplier: Hirsch Industries, Richmond, VA 23230.

Adverse Effects: All adverse effects are allergic in nature and occur in <1% of patients. These

include localized swelling and pruritus of the hands, feet, abdomen and neck. Severe reactions

including edema of the face and glottis, respiratory distress, and shock have been occasionally

reported with other similar compounds. In rare instances, isosulfan blue can cause a transient

drop in oxygen saturation as measured by pulse oximetry. Isosulfan blue will turn the urine

blue-green for up to 24 hours following injection.

Contraindications: Known hypersensitivity to phenylethane compounds.

Methylene Blue

Formulation: Sterile solution of 1% methylene blue in water for injection in 1 ml and 10 ml vials.

Preparation: None.

Storage: Room Temperature (15-25 °C).

Supplier: Taylor Pharmaceuticals, Decatur, IL 62522.

Dose: Up to 4 ml subcutaneous. Not for IV use for this protocol.

Metabolism: Methylene blue is reduced in tissues to leucomethylene blue.

Adverse Effects: Subcutaneous necrosis has been reported at injection sites. In this study the

injection site is resected with the primary tumor. This complication has not been described in

lymphatic mapping studies. Allergic reactions such as rash, hives, or hypersensitivity reactions

have been described. They appear to occur in approximately 1% of patients.

Contraindications: No contraindications for subcutaneous use other than a history of allergic

reaction to this compound.

Drug-lab interactions: Pulse Oximetry: inaccurate and artificially low.

Indocyanine Green (IC-Green™)

• Formulation: 25mg Sterile Indocyanine Green Single-dose Vials and Sterile Aqueous Solvent

Ampoules

Preparation: None

Storage: 20°- 25°C (68°- 77°F)

Supplier: AKORN, Lake Forest, IL 60045

Dose: Up to 10ml subcutaneous. Not for IV use in this protocol

- Adverse Effects: IC-Green™ is non-irritating when administered subcutaneously. In this study
 the injection site is resected with the primary tumor. Anaphylactic or urticarial reactions have
 been reported in patients with or without history of allergy to iodides. Treatment with
 appropriate agents, e.g. epinephrine, antihistamines and corticosteroids should be
 administered.
- Contraindications: IC-Green[™] contains sodium iodide and should be used with caution with those with a history of allergies to iodides.
- Drug-lab interactions: Heparin preparations containing sodium bisulfite reduce the absorption peak of IC-Green™ in blood and therefore should not be used as an anticoagulant for the collection of samples for analyses. Radioactive iodine uptake studies should not be performed for at least a week following the uses of IC-Green™.

4.0 PATIENT ELIGIBILITY AND EXCLUSIONS

4.1 INCLUSION CRITERIA

- Histologically confirmed primary adenocarcinoma, squamous cell carcinoma or adenosquamous carcinoma of the uterine cervix;
- Patients with Histologically confirmed stage IA1 (with lymph vascular invasion), stage IA2, or stage IB1 disease
- 3. Patients undergoing either a Type II or III radical hysterectomy (Piver Classification)
- 4. Patients with adequate bone marrow, renal & hepatic function using Standard International Units:
 - 4.1 WBC > 3.0x109 cells/L
 - 4.2 Platelets >100x109 cells/L
 - 4.3 Creatinine <180 µmmol/L (non-IDMS)
 - 4.4 Bilirubin <1.5 x normal and AST/SGOT or ALT/SGPT <3 x normal
- 5. ECOG Performance Status of 0 or 1.
- 6. Patients must be suitable candidates for surgery.
- 7. Patients who have signed an approved Informed Consent
- 8. Patients with a prior malignancy allowed if > 5 years ago with no current evidence of disease
- 9. Females, aged 18 years or older
- 10. Negative serum pregnancy test ≤ 30 days of surgery in pre-menopausal women and women< 2 years after the onset of menopause

4.2 EXCLUSION CRITERIA

- 1. Any histology other than adenocarcinoma, squamous cell carcinoma or adenosquamous carcinoma of the uterine cervix;
- 2. Tumor size greater than 4 cm;
- 3. FIGO stage II-IV;
- 4. Patients with a history of pelvic or abdominal radiotherapy;
- 5. Patients who are pregnant;
- 6. Patients with contraindications to surgery;
- 7. Patients with evidence of metastatic disease by conventional imaging studies, enlarged pelvic or aortic lymph nodes > 2cm; or histologically positive lymph nodes
- Unfit for Surgery: serious concomitant systemic disorders incompatible with the study (at the discretion of the investigator);
- 9. Patients unable to withstand prolonged lithotomy and steep Trendelenburg position
- 10. Patient compliance and geographic proximity that do not allow adequate follow-up
- 12 Patients who agree to IOLM must not have:
 - Known allergies to triphenylmethane compounds.
 - A history of retroperitoneal surgery.
 - A history of pelvic irradiation.
 - A cold knife or LEEP cone biopsy within 4 wks of enrollment.

5.0 STUDY DESIGN

This Phase III international, multi-centre, open-label, randomized clinical trial design is an equivalence study with the hypothesis that TARH is equivalent TLRH in terms of disease free survival (DFS). The study will be conducted in two stages.

5.1 STAGE 1

The first stage will assess feasibility of recruitment and delivery of the intervention and collect quality of life on the first 100 patients.

5.2 STAGE 2

The Trial Management Committee (refer to Section 19.2) will decide whether the trial will progress along Option 1 or Option 2 based on clinical and economical feasibility and the level of interest amongst the clinical community.

[figure not shown]
Option 1

A randomized equivalence trial with disease-free survival as the endpoint is the definitive means of determining whether TLRH is at least equivalent to TARH. As such, it is planned to extend the trial to a larger randomized equivalence clinical trial (additional 640 patients) assessing disease free survival at 4.5 years from surgery.

Option 2

The study will follow-up the cohort of patients who had received a total laparoscopic or robotic radical hysterectomy for a minimum of 4.5 years post-surgery to determine whether the estimate of disease-free survival for patients who undergo laparoscopic or robotic surgery is consistent with the (control group) four-year disease-free survival rate of 90%.

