| APPEND | DIX 10: TRANSLATION FORMS FOR SOURCE DATA FOR NON-ENGLISH SPEAKING SITES | .89 |
| DEEEDE | NCFS | 00 |

PROTOCOL SYNOPSIS

| Protocol Title | LACC - Laparoscopic Approach to Cervical Cancer | | |
|-------------------------|-----------------------------------------------------------------------------------------------------------------------------------------------------------------------------------------------------------------------------------------------------------------------------------------------------------------------------------------------------------------------------------------------------------------------------------------------------------------------|--|--|
| Full Protocol Title | A Phase III Randomized Clinical Trial Comparing Laparoscopic or Robotic Radical Hysterectomy versus Abdominal Radical Hysterectomy in Patients with Early Stage Cervical Cancer | | |
| Indication | Cervical Cancer - FIGO Stage 1A, FIGO Stage 1B1 (as determined by the following examinations: Cervical biopsy/cone biopsy, PV/PR examination, EUA, xray) | | |
| Primary Objective | To compare disease-free survival amongst patients who undergo a total laparoscopic or robotic radical hysterectomy (TLRH) versus those who undergo a total abdominal radical hysterectomy (TARH) for early stage cervical cancer. | | |
| Secondary Objectives | Compare patterns of recurrence between arms. Compare treatment-associated morbidity within 6 months from surgery. Compare the cost effectiveness of TLRH or TRRH versus TARH Compare the impact on Quality of Life (QoL) between arms. Assess pelvic floor function Compare overall survival between arms Determine the feasibility of sentinel lymph node biopsy in this group of patients | | |
| Study Design | International Multicenter Randomized 1:1 Phase III Two-Stage Clinical Trial Stratification for Site and FIGO Stage. | | |
| Stage 1 | The first stage will assess feasibility of recruitment and delivery of the intervention and collect quality of life on the first 100 patients | | |
| Stage 2 | Should the trial be extended, the Trial Management Committee will select one of the following options: Option #1: The disease-free survival at 4.5 years of the TLRH group is compared against the control group disease-free survival rate Option #2: The trial is expanded to a larger randomized equivalence clinical trial (additional 640 patients) assessing disease-free survival at 4.5 years from treatment | | |

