| Planned Sample Size | Phase 1: 100 participants randomized 1:1 (50 TLRH/TRRH: 50 TARH) Phase 2: Additional 640 participants randomized 1:1 (320 TLRH/TRRH: 320 TARH) | | |

Inclusion Criteria

- 1 Histologically confirmed primary adenocarcinoma, squamous cell carcinoma or adenosquamous carcinoma of the uterine cervix;
- 2 Patients with FIGO stage IA1 (with lymph vascular space invasion), IA2, or IB1 disease;
- Patients undergoing either a Type II or III radical hysterectomy (Piver Classification)
- 4 Patients with adequate bone marrow, renal and hepatic function using Standard International Units:
 - $4.1 \text{ WBC} > 3.0 \text{x} 10^9 \text{ cells/L}$
 - 4.2 Platelets >100x109 cells/L
 - 4.3 Creatinine <180 µmmol/L (non-IDMS)
 - 4.4 Bilirubin <1.5 x normal and AST/SGOT or ALT/SGPT <3 x normal
- 5 Performance status of ECOG 0-1:
- 6 Patient must be suitable candidates for surgery;
- 7 Patients who have signed an approved Informed Consent;
- 8 Patients with a prior malignancy allowed if > 5 years previous with no current evidence of disease:
- 9 Females, aged 18 years or older.
- 10 Negative serum pregnancy test ≤ 30 days of surgery in pre-menopausal women and women < 2 years after the onset of menopause

Exclusion Criteria

- Any histological type other than adenocarcinoma, squamous cell carcinoma or adenosquamous carcinoma of the uterine cervix;
- 2 Tumor size greater than 4 cm;
- 3 FIGO stage II-IV;
- 4 Patients with a history of pelvic or abdominal radiotherapy;
- 5 Patients who are pregnant;
- 6 Patients with contraindications to surgery;
- 7 Patients with evidence of metastatic disease by conventional imaging studies, enlarged pelvic or aortic lymph nodes > 2cm; or histologically positive lymph nodes
- Unfit for Surgery: serious concomitant systemic disorders incompatible with the study (at the discretion of the investigator);
- Patients unable to withstand prolonged lithotomy and steep Trendelenburg position
- 10 Patient compliance and geographic proximity that do not allow adequate follow-up.
- 11 Patients who agree to intra-operative lymphatic mapping (IOLM) must not have:
 - Known allergies to triphenylmethane compounds.
 - History of retroperitoneal surgery.
 - History of pelvic irradiation.
 - Cold knife or LEEP cone biopsy within 4 wks of enrollment.

Standard Treatment

Total Abdominal Radical Hysterectomy (TARH) + / pelvic/ +/- aortic lymph

| | node dissection. | |

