9.0 SAMPLE SIZE

The primary objective of this study is to determine whether Total Laparoscopic (TLRH) or Robotic Radical Hysterectomy (TRRH) is equivalent to Total Abdominal Radical Hysterectomy (TARH) with respect to 4.5 year disease free survival. If the disease free survival does not differ by more than 7% then the two procedures will be considered to be equivalent.

The 4.5 year disease free survival rate for patients undergoing TARH is estimated to be 90%. The following table, based on exponential survival times, gives the sample sizes required for levels of differences in disease free survival rates at 4.5 years. These differences will be regarded as being equivalent based on different accrual and follow-up times. The sample sizes assume a power of 80%, 95% confidence and two-tailed comparisons.

Based on these numbers, for a 4.5-year accrual and 4.5-year follow-up, a total of 740 patients (370 per arm) would be sufficient to declare equivalence with an equivalence margin of 7.2% or less at 4.5 years. If accrual is sufficiently rapid (ie less than 4.5 years), consideration will be given to increasing the sample size to reduce the amount of follow-up required but maintain the equivalence margin. This sample size will have 87% power to detect a non-inferiority margin of the same magnitude.

Table for Option 1 Randomised Design

| 4yr Disease Free Survival difference to be regarded as equivalent | | Years | Total Sample Size | |
|-------------------------------------------------------------------|------|---------|-------------------|------|
| TLRH/TRRH | TARH | Accrual | Follow-up | |
| | | 3 | 3 | 1660 |
| | | 3 | 4 | 1380 |
| 85 | 90 | 3 | 5 | 1190 |
| | | 4 | 4 | 1280 |
| | | 4 | 5 | 1114 |
| | 90 | 3 | 3 | 750 |
| | | 3 | 4 | 760 |
| 84 | | 3 | 5 | 654 |
| 04 | | 4.5 | 4.5 | 740 |
| | | 4 | 5 | 614 |
| | | 5 | 4 | 656 |
| | | 3 | 3 | 794 |
| | | 3 | 4 | 660 |
| 85 | 92 | 3 | 5 56 | |
| | | 4 | 4 | 612 |
| | | 4 | 5 | 532 |

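### The single-arm branch of Stage 2 (5.2 Option 2) judges about 50 TLRH/TRRH patients against a fixed 90% by an undefined criterion and leaves out the concurrent randomised controls; no rule on that number can resolve the 7-point margin

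*Protocol*

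**What the plan says.** Section 5.2 of the protocol gives the Trial Management Committee two ways to run Stage 2, to be chosen on feasibility and clinical interest. Option 1 expands the randomised trial by 640 patients and is described as the definitive route. Option 2 is a single-arm follow-up: "The study will follow-up the cohort of patients who had received a total laparoscopic or robotic radical hysterectomy". Observation lasts at least 4.5 years, and the question is whether the estimate "is consistent with the (control group) four-year disease-free survival rate of 90"%. No test, interval, margin, sample size or error rate is attached to it.

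Three other places bear on this branch.

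- **Synopsis, Stage 2.** The same branch is numbered Option #1 and reads: "The disease-free survival at 4.5 years of the TLRH group is compared against the control group disease-free survival rate". It gives no 90%.
- **Synopsis, Planned Sample Size.** "Phase 1: 100 participants randomized 1:1 (50 TLRH/TRRH: 50 TARH". The additional 640 patients form a separate second phase.
- **Section 9.0.** "The 4.5 year disease free survival rate for patients undergoing TARH is estimated to be 90"%. The margin is set by "If the disease free survival does not differ by more than 7% then the two procedures will be considered to be equivalent". The table there calls the randomised design Option 1, in line with 5.2 and against the synopsis.

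**The concern.** Asking whether an estimate is compatible with a target is not a test of equivalence. The fewer the patients, the wider the interval and the easier it is to be compatible, so the criterion rewards lack of information. Here the cohort is about 50, and the target is the planning value for the control arm, not a rate measured in the trial.

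The trial will hold 50 concurrently randomised TARH patients from the same centres, stages and period. Replacing them with a fixed 90% exposes the result to any gap between the planning value and what open surgery achieves in this population.

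The benchmark is also unstable between sections: a four-year fixed rate in 5.2, the control group rate at 4.5 years in the synopsis, and a 4.5-year 90% in section 9. Because the option numbers are reversed between the synopsis and 5.2, a recorded decision for Option 1 could mean either design.

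**Working it through.** **Inputs.** Cohort of 50 (synopsis, Planned Sample Size). Benchmark 90% (5.2 and 9.0). Margin 7 points (9.0), so its edge is 90 − 7 = 83%. Loss to follow-up taken as zero; 40 to 45 evaluable is used as a sensitivity range.

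**The plan's own sample size first.** Section 9.0 states that 740 patients "would be sufficient to declare equivalence with an equivalence margin of 7.2% or less at 4.5 years". A simple two-sided equivalence formula on proportions, with true rates of 90% in both arms, gives per arm

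n = (1.96 + 1.2816)² × 2 × 0.9 × 0.1 / 0.072² = 365,

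or 730 in total, within 1.4% of 740. At 370 per arm the standard error is √(0.18/370) = 0.0221, and the equivalence power is 2Φ(0.072/0.0221 − 1.96) − 1 = 0.81, against the stated 80%. The margin is thus one that needs about 370 per arm. Section 9.0 makes no matching calculation for the single-arm branch.

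**Reading 1: the 95% interval contains 90% (assumed).** Exact (Clopper-Pearson) limits for n = 50:

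| Disease-free | 95% interval | Contains 90%? |
|---|---|---|
| 40 | 66.3% to 89.97% | No |
| 41 | 68.6% to 91.4% | Yes |
| 49 | 89.4% to 99.9% | Yes |
| 50 | 92.9% to 100% | No |

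So 41 to 49 passes. The pass probability is P(41 ≤ X ≤ 49) with X binomial (50, p):

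| True DFS | P(pass) |
|---|---|
| 90% | 0.970 |
| 83% | 0.660 |
| 82.8% (7.2-point margin) | 0.645 |
| 81% | 0.515 |
| 80.5% | 0.479 |
| 80% | 0.444 |
| 78% | 0.313 |

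**Other readings, at true 83%.**

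- 95% Wilson, Jeffreys or log-log interval: 0.66.
- 95% Wald interval: 0.77.
- Normal-approximation test: 0.60.
- 90% Wilson or Jeffreys interval: 0.52.
- With 40 to 45 evaluable: 0.77 to 0.78 (exact) or 0.63 to 0.65 (Wilson).
- Point estimate of at least 90% (45 or more of 50): 0.126. A true 90% arm then passes 0.616, so it fails 38% of the time.

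**Would a stricter rule rescue 50 patients?** Requiring the exact lower 95% limit to exceed 83% needs 47 of 50 (lower limit 83.5%; 46 gives 80.8%). It passes 2.1% at true 83% and only 25% at true 90%. A single-arm test of 83% against 90%, at one-sided 0.025 and 80% power, needs about 198 patients.

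**What the randomised comparison would give.** For 50 v 50 at 90% each, the 95% half-width is 1.96 × √(2 × 0.9 × 0.1/50) = 0.118, about 12 points. Non-inferiority power at 7 points is Φ(0.07/0.06 − 1.96) = 0.21.

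**Time point.** Under the exponential assumption of section 9.0, 90% at 4 years is 0.9^(4.5/4) = 88.8% at 4.5 years, a shift of 1.2 points. Conversely, 83% at 4.5 years is 0.83^(4/4.5) = 84.7% at 4 years, and a comparison with 90% at 4 years would pass that arm with probability 0.775 under reading 1.

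**The case against.** The protocol does not treat the branches as equals. Section 5.2 calls the randomised trial definitive and says that extending it is the plan. Section 9.0 sizes only that design, 10.1 speaks of going on to 740 patients, and 10.2 describes comparisons between arms. Option 2 states no equivalence claim, and how consistency is tested could be left to a statistical analysis plan. The synopsis wording could be read as using the randomised controls, and the visits in 12.4 are not limited to one arm. Switching to the randomised difference adds no precision: 50 v 50 cannot resolve 7 points either.

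Most of this stands. A reader might infer that the single-arm branch is an equal route to the primary conclusion, or that it would probably report an inferior procedure as equivalent. The documents support neither. An arm at exactly 83% is on the margin, not beyond it, and under the assumed interval rule the pass rate is below half once true DFS is about 80.5% or lower.

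What does not fall away is what the protocol itself fixes: the single-arm cohort, its size of about 50, the fixed benchmark, and the committee's freedom to choose this branch with no statement that it is only descriptive. An analysis plan can define a test but cannot change those.

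**Conclusion.** The point holds as a conditional weakness of one permitted branch. If the committee chooses it, about 50 patients would be judged against a planning value by an undefined criterion, with the concurrent controls left out. Under the assumed 95% interval rule, an arm at the edge of the margin passes about 66% of the time, with a range of about 0.5 to 0.8 over other interval or test readings. The 13% under a point-estimate rule comes at the price of failing a true 90% arm 38% of the time. It would be tempting to quote two in three as a property of the protocol; it is a property of one assumed reading.

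The firmer conclusion does not depend on the reading: no rule on about 50 patients separates 90% from 83% with acceptable error in both directions. The disagreements over comparator, time point and option number stand without any calculation. The four-year label also heads the section 9.0 table, so that mismatch is not confined to 5.2.

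**What to change.** In section 5.2, Option 2:

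1. Replace the comparison with a fixed 90% by follow-up of both randomised arms to 4.5 years, and report the randomised difference in 4.5-year Kaplan-Meier DFS with its 95% confidence interval. State the expected half-width of about 12 points.
2. State that this branch is descriptive and cannot establish equivalence within the 7-point margin.
3. Reconcile the synopsis, 5.2 and 9.0 on the time point (4 or 4.5 years), the comparator, and which design is Option 1.

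The cost is protocol wording. No patients are added, and the visit schedule in 12.4 already runs to 4.5 years for both arms. The gain is the concurrent control and honest labelling, not precision. The downside is that this branch could no longer support an equivalence claim.
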